**Figure AMAM.1.1**

**Study schema.**

## 2 Statistical Hypothesis

The primary efficacy objective is to summarize the proportion of participants who achieve the co-primary endpoints, as described in Section 1.1.

### 2.1 Multiplicity Adjustment

Only descriptive summaries of select efficacy endpoints will be provided due to the early stoppage of enrollment of adolescent participants in Study AMAM. Thus, no multiplicity adjustment is required.

### 3 Sample Size Determination

Approximately [REDACTED] participants were planned to be screened to achieve at least [REDACTED] participants assigned to study intervention and receive study intervention. After 6 participants were enrolled, the sponsor elected to stop enrollment of adolescents in Study AMAM and enroll pediatric participants in a separate, stand-alone study. The 6 enrolled participants were allowed to continue treatment and finish the study. Enrolled patients had the opportunity to continue to the long-term extension Study AMAZ if deemed eligible after completing Study AMAM.

All patients enrolled are assigned to mirikizumab.

## 4 Analysis Sets

For purposes of analysis, the following analysis sets are defined in [Table AMAM.4.1](#).

[Table AMAM.4.1. Populations for Analysis](#)

Population	Description
Screening Population	Definition: All participants who signed informed consent. Purpose: Used for disposition analysis.
Modified Intent-to-Treat (mITT) Population	Definition: All patients from the ITT population who take at least 1 dose of study intervention, even if the participant does not take the assigned study intervention, does not receive the correct study intervention, or otherwise does not follow the protocol. Purpose: Used for efficacy related analysis.
Safety Population	Definition: Same as mITT Population. Purpose: Safety analyses will be conducted on this population.

## 5 Statistical Analyses

### 5.1 General Considerations

Statistical analysis of this study will be the responsibility of Lilly or its designee.

Not all displays and analyses described in this SAP will necessarily be included in the clinical study report (CSR). Not all displays will necessarily be created as a “static” display. Some displays may be incorporated as interactive display tools such as Spotfire instead of or in addition to a static display. Any display described in this SAP and not provided in the CSR would be available upon request.

Unless otherwise specified, efficacy analyses will be conducted on the mITT population, and safety analyses will be conducted on the safety population as described in Section 4.

When reported, descriptive statistics will include the number of participants, mean, standard deviation, minimum, first quartile, median, third quartile, and maximum for continuous measures, and frequency counts and percentages for categorical measures.

Any change to the data analysis methods described in the addendum to the protocol for adolescents will require a protocol amendment ONLY if it changes a principal feature of the addendum. Any other change to the data analysis methods described in the addendum and the justification for making the change will be described in the CSR.

Additional exploratory analyses of the data may be conducted as deemed appropriate. Some of these additional supplementary analyses may be prespecified in a separate document.

#### 5.1.1 Analysis Methods

For assessments of categorical endpoints, proportions of participants achieving the endpoint will be provided. For assessments of continuous endpoints, descriptive statistics will be provided for each specified visit, including mean and mean change from baseline. Where appropriate corresponding 95% CIs using the Wilson method (Wilson 1927) will be provided at each applicable visit.

#### 5.1.2 Definition of Baseline

Visit 2 (Week 0) is the baseline treatment assignment visit. The centrally read baseline Simple Endoscopic Score for Crohn’s Disease (SES-CD) score from the screening endoscopy is considered the baseline for endoscopic response and endoscopic remission endpoints. Daily diary entries obtained prior to the first dose of study intervention are also considered as baseline for diary-related endpoints. The baseline score for daily diary entries will be calculated by averaging the most recent 7 days (possibly nonconsecutive) in the 12 days prior to the day of the first dose of study intervention, after removing the day(s) of the endoscopy prep, the day of endoscopy procedure, and the 2 days following the endoscopy procedure. If less than 4 days of data are available, the baseline score will be set to missing. For other efficacy assessments, baseline is defined as the last nonmissing assessment recorded on or prior to the date of the first dose of study intervention (Period 1 start date), unless otherwise specified.

Baseline for safety analysis is described in Section 5.6.

Change from baseline will be calculated as the visit value of interest minus the baseline value. If a baseline values or the value at the visit is missing for a particular variable, then the change from baseline is defined as missing.

### 5.1.3 Definition of Study Period Time Interval

**Table AMAM.5.1** displays a list of study periods along with the definition of which participants will be considered to have entered the study period and when the individuals start and end the study period. The table shows both a date and a time.

To calculate the length of any time interval or time period in this study the following formula will be used:

$$\text{Length of interval (days)} = \text{End Date} - \text{Interval Start Date} + 1$$

To convert any time length from days to years, the following formula will be used:

$$\text{Length of interval (years)} = \text{Length of interval (days)} / 365.25$$

To convert any time length from days to weeks, the following formula will be used:

$$\text{Length of interval (weeks)} = \text{Length of interval (days)} / 7$$

Only for the purpose of calculating the length of study period time intervals, the words “prior to” in **Table AMAM.5.1** should be understood to mean “the day before” while the words “after” should be understood to mean “the day after.” For the purpose of determining whether a date/time lies within an interval these words are intended to convey whether the start or end of the period is inclusive of the specified date.

**Table AMAM.5.1. Study Period Definitions**

Study Period	Interval Start Definition	Interval End Definition
Screening	Informed consent date	Prior to the start of Period 1.
Period 1	At the date/time a of first dose of study intervention. For participants who are assigned treatment but not dosed, Period 1 starts on the date of treatment assignment.	Prior to the start of Period 2. For participants who discontinue before or on the Week 12 visit, Period 1 ends at the latest date of 1) study intervention discontinued date or 2) last study intervention visit date.
Period 2	At the Week 12 dosing date/time a . If the participant is unable to be dosed at the Week 12 visit, the Period 2 starts at the Week 12 Visit. If the participant misses the Week 12 visit, the Period 2 starts at Day 91.	After the Week 52 visit date. For participants who discontinue prior to Week 52, Period 2 ends at the latest date of 1) study intervention disposition date or 2) last study intervention visit date.
Study Treatment Period	Same as Period 1 interval start	The latest of the following dates: (1) the end of the Period 1, (2) the end of the Period 2.

Follow-up Period	All participants who had Visit 801 or Visit 802 are considered to have entered the Follow-up Period. The latest of Period 1 or Period 2 interval end date.	The last date of the last study visit and study disposition date.
-------------------------	------------------------------------------------------------------------------------------------------------------------------------------------------------	-------------------------------------------------------------------

a Missing dose time will be imputed as the earliest time that is consistent with available data about dose time. For example, suppose the minutes are missing but hour is present. In this case, we would impute the minutes to be 0.

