#### Participant Visit Scheme

Study participants will undergo screening assessments, be assigned to treatment with investigational product, and participate **CCI** [REDACTED] if they do not proceed to the long-term extension Study AMAZ.

Screening may be done on more than 1 day, as long as all activities are completed within **CCI** [REDACTED] It is required that sites have received and reviewed all the screening laboratory test results, as well as screening endoscopy results, prior to treatment assignment and dosing at V2. Please note that laboratory results could take **CCI** [REDACTED]  
[REDACTED]

After screening and baseline visits, participants will receive their assigned therapy during the 52-week treatment period (Visits 2 to 17). Period 1 is from Weeks 0 to 12. Period 2 encompasses Weeks 12 to 52. Dosing visits are as specified in the SoA (Section 1.3).

Participants who complete Study AMAM adolescent addendum through **CCI** [REDACTED] will be given the option to enroll in Study AMAZ if they are eligible (Section 6.7.1). With sponsor approval, additional dosing at **CCI** [REDACTED] may occur as needed for participants eligible to enroll in Study AMAZ where the clinical trial site is not yet open. Participants must have completed all procedures at **CCI** [REDACTED]

CCI from the prior dose. Urine pregnancy test must be negative prior to study drug administration. Refer to study AMAZ main protocol inclusion criteria for participants moving into study AMAZ.

Participants who do not meet enrollment criteria for Study AMAZ or who do not choose to participate in Study AMAZ will continue for CCI follow-up visits in Study AMAM.

CCI

Participants who permanently discontinue study drug early will undergo early termination procedures, including an ETV and the post-treatment follow-up visits (Section 7.1).

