## 1.2 Study Design

This open-label addendum to the AMAM adult study will assess efficacy and safety of mirikizumab in the induction and maintenance of remission in adolescents (15 to <18 years of age) with moderately to severely active CD. See Schema below.

Addendum participants with moderate-to-severe CD are unblinded to treatment for the full duration of the study, though the study material assigned and dispensed is blinded. Participants will receive 900 mg mirikizumab by intravenous (IV) infusion doses at Weeks 0, 4, and 8. In the maintenance period, participants will receive 300 mg mirikizumab by SC injection every 4 weeks until Week 48.

The maximum total duration of study participation for each participant, including screening and the post-treatment follow-up period, is 73 weeks.

[figure not shown]
Adolescents who complete Study AMAM Adolescent Addendum through Visit 17 will be given the option to enroll in study (I6T-MC-AMAZ [AMAZ]) if they are eligible. Participants who do not meet enrollment criteria for Study AMAZ or who do not choose to participate in Study AMAZ will return for 2 post-treatment follow-up visits in Study AMAM (V801 and V802).

Study intervention may be permanently discontinued or temporarily withheld during the study (see Sections 7.1.1 and 7.1.2 of the AMAM Adolescent Addendum). Participants who permanently discontinue study drug early will undergo early termination procedures, which include an early termination visit (ETV) and post-treatment follow-up visits (V801 and V802).

No rescue medication is allowed during the study. Participants who achieve clinical response and who are currently on corticosteroids will initiate corticosteroid tapering at or after Week 12, as described in the protocol (see Section 6.5.3 of the AMAM Adolescent Addendum).

No efficacy interim analyses are planned. A Data Monitoring Committee (DMC) consisting of members external to Lilly will be established for interim safety monitoring across all the sponsor's Phase 3 studies in participants with CD. Additional details can be found in the DMC Charter.

Primary analyses will be performed at database lock after all adolescents and all adult participants have completed Week 52 (Visit 17) assessments or ETV. Final analyses will be performed at database lock after Last Participant Last Visit.

Abbreviations: IV = intravenous; mg = milligram; SC = subcutaneous.

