## 5.3 Primary Endpoint(s) Analysis

### 5.3.1 Definition of Endpoint(s)

The co-primary endpoints are comprised of 2 separate endpoints:

- the proportion of participants achieving clinical response at Week 12 **CCI** and endoscopic response at Week 52, and
- the proportion of participants achieving clinical response at Week 12 **CCI** and clinical remission **CCI** at Week 52.

Descriptions and derivations of these endpoints are shown in [Appendix 1](#).

Endoscopies performed for Week 52 that occur up to a maximum of 14 days after the Week 52 visit date, but before any additional dosing, will be used for the analysis of Week 52.

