3. CCI [REDACTED]
4. CCI [REDACTED]

## 6.10 Appendix 10: Study Visit or Week Definition for Daily Diary

CDAI-SF, CDAI-AP, CDAI Well-Being, Urgency NRS and additional measures are collected using Patient Daily Diary, entries will be mapped to study week by the following:

Visit Number / Week Number	Start Day	End Day
Visit 2 / Baseline	Date of First Injection -12 days	Date of First Injection – 1 day
Visit 3 / Week 2	Max (Date of First Injection, Week 2 Assessment Date – 12 days)	Week 2 Assessment Date – 1 day
Visit 4 / Week 4	Max (Week 2 Assessment Date, Week 4 Assessment Date – 12 days)	Week 4 Assessment Date – 1 day
Visit 5 / Week 6	Max (Week 4 Assessment Date, Week 6 Assessment Date – 12 days)	Week 6 Assessment Date – 1 day
Visit 6 / Week 8	Max (Week 6 Assessment Date, Week 8 Assessment Date – 12 days)	Week 8 Assessment Date – 1 day
Visit 7 / Week 12	Max (Week 8 Assessment Date, Min (Week 12 Assessment Date, Start date of Period 2) – 12 days)	Min (Week 12 Assessment Date, Start date of Period 2) – 1 day
Visit 8 / Week 16	Max (Week 12 Assessment Date (i.e. Date of First Injection of Period 2), Week 16 Assessment Date – 12 days)	Week 16 Assessment Date – 1 day
Visit 9 / Week 20	Max (Week 16 Assessment Date, Week 20 Assessment Date – 12 days)	Week 20 Assessment Date – 1 day
Visit 10 / Week 24	Max (Week 20 Assessment Date, Week 24 Assessment Date – 12 days)	Week 24 Assessment Date – 1 day
Visit 11 / Week 28	Max (Week 24 Assessment Date, Week 28 Assessment Date – 12 days)	Week 28 Assessment Date – 1 day
Visit 12 / Week 32	Max (Week 28 Assessment Date, Week 32 Assessment Date – 12 days)	Week 32 Assessment Date – 1 day
Visit 13 / Week 36	Max (Week 32 Assessment Date, Week 36 Assessment Date – 12 days)	Week 36 Assessment Date – 1 day
Visit 14 / Week 40	Max (Week 36 Assessment Date, Week 40 Assessment Date – 12 days)	Week 40 Assessment Date – 1 day
Visit 15 / Week 44	Max (Week 40 Assessment Date, Week 44 Assessment Date – 12 days)	Week 44 Assessment Date – 1 day
Visit 16 / Week 48	Max (Week 44 Assessment Date, Week 48 Assessment Date – 12 days)	Week 48 Assessment Date – 1 day
Visit 17 / Week 52	Max (Week 48 Assessment Date, Week 52 Assessment Date – 12 days)	Week 52 Assessment Date – 1 day

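### Table AMAM.5.1 closes the safety period for completers at the Week 52 visit, so if additional AMAM doses were given before Study AMAZ entry, on-drug time and some safety data fall outside the planned outputs

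*SAP*

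**What the plan says.** Protocol 4.1 (Participant Visit Scheme) states that, with sponsor approval, additional dosing "may occur as needed for participants eligible to enroll in Study AMAZ where the clinical trial site is not yet open". The visit and spacing of these doses are redacted.

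SAP Table AMAM.5.1 ends Period 2 as follows: "After the Week 52 visit date. For participants who discontinue prior to Week 52, Period 2 ends at the latest date of" the disposition from study drug or the last on-treatment visit. The later-date rule therefore serves early discontinuers only. The Study Treatment Period ends at the later of the Period 1 and Period 2 ends, with no term for a later dose. On the Follow-up Period the table says: "All participants who had Visit 801 or Visit 802 are considered to have entered the Follow-up Period". SAP 1.2 assigns those two visits to completers who are not going on to the extension: participants who are ineligible or "who do not choose to participate in Study AMAZ will return for 2 post-treatment follow-up visits in Study AMAM".

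The safety outputs take their windows from these definitions:
- Exposure (SAP 5.6.1) uses the Study Treatment Period.
- AE summaries (SAP 5.6.2) use that period alone, or that period plus the Follow-up Period.
- Laboratory displays (SAP 5.6.3), the ALT/AST and bilirubin/ALP threshold listings (SAP 5.6.7.1) and, by default, the listings of adverse events of special interest (SAP 5.6.7) are limited to the treatment period.
- The general listing of follow-up safety data (SAP 5.6) covers only those who do not enter AMAZ.

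**The concern.** The provision is written for participants who finish AMAM, stay on drug and move into the extension without the post-treatment visits. The period definitions do not fit that group. Their time on an additional dose belongs to no treatment period, and they have no Follow-up Period to fall back on.

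The SAP does refer to dosing after Week 52. SAP 5.3.1 accepts Week 52 endoscopies "that occur up to a maximum of 14 days after the Week 52 visit date, but before any additional dosing". It gives no corresponding rule for safety.

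With six participants and a purely descriptive report, complete safety accounting is one of the main things the addendum can deliver. At stake are the patient-years total and the visibility, in the AE and laboratory outputs, of non-serious events and abnormal values that arise on drug. The data are collected either way, so the gap is one of display.

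**Working it through.** **1. When the additional doses can occur.** The timing is redacted, so it has to be inferred. SAP 1.2: "Adolescents who complete Study AMAM Adolescent Addendum through Visit 17 will be given the option to enroll in study". SAP Appendix 10 labels that visit "Visit 17 / Week 52". Recipients must therefore be Week 52 completers, which puts the dose at or after Week 52. The endoscopy rule in SAP 5.3.1 points the same way but is weaker, because it does not say that the dosing is in AMAM.

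**2. Counted time for a completer.** Assume Day 1 is the first dose and the Week *w* visit falls on Day 7*w* + 1 (the day row of the Schedule of Activities is not visible).
- Planned duration: 12 + 40 = 52 weeks, which agrees with Protocol 4.1.
- Week 52 visit: 7 × 52 + 1 = Day 365.
- SAP 5.1.3 says that, for interval length only, the word after means the following day, so the end is Day 366.
- Length = End − Start + 1 = 366 − 1 + 1 = 366 days, or 366/7 = 52.3 weeks.

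This figure is the same whatever is dosed later.

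**3. Time missed per additional dose.** Assume one dose at the Week 52 visit (Day 365), with AMAM time ending at AMAZ entry. The interval to entry is an assumption; 28 days mirrors Week 48 to Week 52.

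| AMAZ entry after dose | Last AMAM day | Counted | Missed | Patient-years (÷ 365.25) | % of 366 counted days |
|---|---|---|---|---|---|
| 28 days | 393 | 366 | 27 | 0.074 | 7.4 |
| 14 days | 379 | 366 | 13 | 0.036 | 3.6 |
| 0 or 1 day | 365 or 366 | 365 or 366 | 0 | 0 | 0 |

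Later or repeated doses would add to this. No total is given for the cohort, because the documents give no number of doses or recipients.

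**4. Where an adverse event falls.** For deciding whether a date lies inside a period, SAP 5.1.3 says "these words are intended to convey whether the start or end of the period is inclusive of the specified date". The Week 52 visit date is therefore inside and later dates are outside.

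| Onset | V801 or V802? | Treatment period alone | Treatment plus follow-up |
|---|---|---|---|
| Up to Day 365 | either | yes | yes |
| Day 366 on | yes | no | yes |
| Day 366 on | no | no | no |

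The last row is the recipient who enters AMAZ directly. The SAP 5.6 follow-up listing does not pick this participant up either.

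**5. What is not cut at Week 52.** Deaths are listed to the end of participation, and the SAE listing states no period (SAP 5.6.2.1). Vital signs (5.6.4), immunogenicity (5.6.6), the Hepatic-Safety form listing (5.6.7.1) and injection or infusion site reactions (5.6.7.4) also state none. Cerebro-cardiovascular events and malignancies are listed whenever they occur (5.6.7.5, 5.6.7.6). The registry summary in Appendix 6 covers both serious and other events, again with no stated period. What remains exposed is the other non-serious events in the AE tables, the default special-interest listings (for example non-serious infections and hypersensitivity), the laboratory displays and the hepatic-threshold listings.

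**The case against.** The strongest reply is that the problem may never have arisen. No passage shows that any participant received an additional dose. The dosing text in Protocol 4.1 is partly redacted, and so is a footnote to the Schedule of Activities that begins with sponsor approval and may govern the same provision. The compound level safety standards to which the SAP defers are not available, so a rule there cannot be excluded. The top exposure category is already 48 weeks or more, so category counts for nominal completers would not change. All of this stands, and it is why the point is conditional and minor.

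Protocol Appendix 12 says that the length of exposure will not be extended. That text governs temporary visit-window changes in exceptional circumstances and does not withdraw the provision in Protocol 4.1.

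A reader might infer more than the documents support:
- *That exposure is undercounted for every recipient.* It is not if AMAM time ends on the Week 52 visit date or the day after.
- *That the non-serious events vanish from all AMAM reporting.* The registry summary of other events states no period limit, so they may appear there. It also calls for consistency with the study report, so their inclusion is not certain.
- *That the protocol contradicts itself* by giving Week 48 as the last maintenance dose and up to 52 weeks of treatment. Those sections state the standard schedule, and Protocol 4.1 adds an express, sponsor-approved exception.

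**Conclusion.** The gap is real but conditional and minor. Table AMAM.5.1 is unredacted and gives a definite end for completers. Followed as written, it leaves out on-drug time whenever an additional dose is given and AMAM time continues beyond the day after the Week 52 visit.

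The consequence depends on the route out of AMAM. Recipients who enter AMAZ without V801 or V802 lose the exposure time, the period-limited laboratory and special-interest displays, and a place for later non-serious events in either AE analysis period. Recipients who do have those visits lose the exposure time; their later events reach the combined AE summary, labelled as follow-up, and their follow-up safety data are listed.

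The size is that of step 3 for each dose and rests on an assumed dose date and interval to AMAZ entry; it is zero if no additional dose was given. Timing at or after Week 52 is inferred, mainly from SAP 1.2 and Appendix 10. Week 52 efficacy results do not change.

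**What to change.** Keep Period 2 and every Week 52 window as they are. For anyone given an additional AMAM dose, add one by-participant listing of all AMAM dosing, adverse events and laboratory data after the Week 52 visit, and report the additional exposure time beside the main total.

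Alternatively, for these participants only, define a safety-only end of the Study Treatment Period: AMAZ entry, or V801 or the end of AMAM participation if they do not enter AMAZ, and never earlier than the last additional AMAM dose. That floor matters, because a disposition recorded at Visit 17 could otherwise pull the date back to Week 52. Use this date for exposure, treatment-emergent AE, laboratory, hepatic and special-interest outputs. Moving Period 2 itself would also shift the listings of Crohn's-related emergency visits, hospitalizations and surgeries in SAP 5.7, which is why the date should be for safety only.

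If no additional dose was given, say so in the clinical study report and change nothing else.

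The cost is one listing, or one date derived from data already collected. There is no new data collection and no effect on participants.

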### 5.6.1 Extent of Exposure

Duration of exposure to study intervention will be summarized for the safety analysis population in the Study Treatment Period. Exposure will be calculated as (Date of end date in the Interval – Date of start date in the Interval + 1 day). Total patient-years of exposure will be reported including all adolescents in the safety analysis population.

Descriptive statistics will be provided for participants-weeks of exposure and the frequency of participants falling into different exposure ranges will be summarized.

- $\geq 0$ ,  $\geq 4$  weeks,  $\geq 8$  weeks,  $\geq 12$  weeks,  $\geq 16$  weeks,  $\geq 24$  weeks,  $\geq 32$  weeks,  $\geq 40$  weeks,  $\geq 48$  weeks.

- >0 to <4 weeks, ≥4 weeks to <8 weeks, ≥8 weeks to <12 weeks, ≥12 weeks to 16 weeks, ..., ≥48 weeks

Additional exposure ranges may be considered if necessary.

Reasons for not taking study intervention and reasons for not taking the planned amount of study intervention will be reviewed.

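### SAP 5.1.3 pairs a day-after end point with an inclusive length formula, so each completer's treatment-period length is one day above the inclusive count; the effect is confined to the descriptive exposure summary

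*SAP*

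**What the plan says.** SAP 5.1.3 defines the length of any interval as end date minus start date plus 1. It then adds a reading rule for two words in Table AMAM.5.1. The rule applies "Only for the purpose of calculating the length of study period time intervals". For that purpose the words *prior to* "should be understood to mean “the day before” while the words “after” should be understood to mean “the day after". For the separate purpose of deciding whether a date falls inside an interval, "these words are intended to convey whether the start or end of the period is inclusive of the specified date".

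In the table, the entry for the end of Period 2 reads "After the Week 52 visit date. For participants who discontinue prior to Week 52, Period 2 ends at the latest date of" and then gives two actual dates, the disposition date and the last treatment visit. Its first sentence governs completers and its second those who stop during Period 2. Participants who stop by Week 12 likewise have Period 1 closed on an actual date. The Study Treatment Period ends at the later of the two period ends. The Follow-up Period starts on that same end date.

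SAP 5.6.1 measures exposure over the Study Treatment Period: "Exposure will be calculated as (Date of end date in the Interval" minus the interval's start date, plus 1 day. From this come duration, participant-weeks, exposure ranges and total patient-years.

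**The concern.** End minus start plus 1 is the right formula when the end date is the last day that belongs to the interval. An end point set to the next day is the right convention when nothing is added. Using both counts one day twice over.

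The table does this at one boundary only. *Prior to*, read as the day before, works with the formula at the ends of Screening and Period 1. The completers' end of Period 2 is the only boundary that uses *after*, and the only one that over-counts. Completers and early stoppers are then measured by different conventions within one summary. What is at stake is the internal consistency of the reported exposure, and whether two programmers working from the same text would get the same number.

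**Working it through.** The documents state no exposure total, so there is no figure to reproduce. The check applies the SAP's rule and compares it with a direct count of days.

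**Inputs**
- Length = end − start + 1; for lengths, *after* = +1 day and *prior to* = −1 day (SAP 5.1.3).
- Period ends as in Table AMAM.5.1.
- Six participants enrolled (SAP 3).
- Years = days / 365.25; weeks = days / 7 (SAP 5.1.3).
- Highest exposure range starts at 48 weeks = 48 × 7 = 336 days (SAP 5.6.1).
- Assumption: the first dose is on Day 1, and Weeks 12 and 52 fall 84 and 364 days later, on Days 85 and 365.

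**Completer, rule as written**
- Period 1: end = 85 − 1 = Day 84; length = 84 − 1 + 1 = 84 days.
- Period 2: end = 365 + 1 = Day 366; length = 366 − 85 + 1 = 282 days.
- Study Treatment Period: 366 − 1 + 1 = 366 days = 84 + 282 (52.29 weeks).

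**Completer, inclusive count through the Week 52 visit**
- Period 2: 365 − 85 + 1 = 281 days.
- Study Treatment Period: 365 − 1 + 1 = 365 days (52.14 weeks).
- Excess under the rule: 366 − 365 = 1 day, or 1/365 = 0.27%. The one-day excess is the same whatever day the Week 52 visit takes place.

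**Early stoppers**

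| Last date, days after first dose | Rule as written | Direct count |
|---|---|---|
| 30 | 31 | 31 |
| 84 | 85 | 85 |
| 200 | 201 | 201 |

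There is no excess.

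**Total if all six complete on schedule**
- As written: 6 × 366 / 365.25 = 6.012 patient-years.
- Inclusive: 6 × 365 / 365.25 = 5.996 patient-years.
- Difference: 6 / 365.25 = 0.016 patient-years.

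**Exposure ranges**

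Both 365 and 366 days lie above 336. The extra day changes a completer's range at 48 weeks only if the inclusive length is 335 days and the rule's length 336. That needs a Week 52 visit on Day 335, before the nominal Week 48 visit on Day 337 (336 + 1).

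**Follow-up row**

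Follow-up starts on the treatment period's end date. As written, a completer's shared day is the day after the Week 52 visit, and an early stopper's is the actual end date. If only the Period 2 entry were changed, the completer's shared day would move to the Week 52 visit itself.

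**The case against.** The strongest reply is that this is a convention with almost no consequence, and most of that stands. The length feeds only a descriptive summary. Adverse event tables in SAP 5.6.2 give numbers and percentages of participants, special safety topics are mostly listed, and the registry output in SAP Appendix 6 uses participants at risk and event counts. No exposure-adjusted rate is planned. There is one treatment group, so no between-group comparison of exposure can be biased. The last injection is at Week 48, so closing the period around Week 52 is itself an observation-window choice, and an early stopper's administrative end date could vary by more than a day.

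A second reply is that *after* merely signals that the Week 52 date is included. That does not hold. SAP 5.1.3 gives that meaning to the membership question and prescribes the next day for lengths.

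Three stronger readings are tempting and not supported:
- A reader might infer that reported exposure contradicts its own dates. It would agree with the end date the SAP defines; that definition is one day later than an inclusive count needs.
- A reader might infer that the length rule and the membership rule contradict each other. SAP 5.1.3 states openly that the words serve two purposes.
- A reader might infer that events are assigned to the wrong period. For membership the Week 52 date is inside Period 2, and the length clause moves no event.

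**Conclusion.** The point holds as a wording fault in a derivation rule. Followed literally, SAP 5.1.3 and Table AMAM.5.1 give each completer a Period 2 and Study Treatment Period one day longer than the inclusive count through the Week 52 visit, while early stoppers get the inclusive count. That one-day excess rests on the text alone.

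The 366 and 365 day figures assume on-schedule visits. The total of 6.012 versus 5.996 patient-years also assumes that all six participants complete, which the documents do not state. Six days is the upper limit, and fewer completers would make it smaller. No efficacy result, adverse event count or on-schedule exposure range changes. It is worth correcting because the correction is cheap and makes the derivation unambiguous; it is not a threat to any conclusion.

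**What to change.** Make three changes together:

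1. In Table AMAM.5.1, end Period 2 for completers on the Week 52 visit date, inclusive.
2. In SAP 5.1.3, delete the clause that reads *after* as the following day. No other boundary in the table uses the word, so nothing else there depends on it. The clause on *prior to* stays.
3. In the Follow-up row, start the period on the day after the latest of the Period 1 or Period 2 end date.

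The third change is needed because the first two alone would leave treatment and follow-up sharing the Week 52 visit day for completers, and would leave the existing shared day for early stoppers.

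The cost is three short wording edits and the matching lines of derivation code for exposure and the follow-up start. Reported exposure falls by one day per completer compared with a literal reading of the present text. No new data are needed.
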